We proposed a 7 year prospective observational study which got extended to 12 years, including 6 months for initiation, 30 months for patient enrollment, 42 months (additional) to complete all patient follow-ups, and 6 months for statistical analyses and manuscript preparation. The proposed study will enroll 550 elective non-cardiac surgical patients, each of whom will be followed prospectively for a minimum of 18 months and up to 72 months initially and then extended to 12 years, after their initial hospitalization. All patients will undergo a baseline evaluation prior to hospitalization, including neuropsychological and frailty testing. The primary outcomes for this project are cognitive decline, based on a neuropsychological test battery, and functional decline. When admitted for the index hospitalization, patients will be assessed daily for the development of delirium, the major predictor variable. Subsequently, each patient will be followed prospectively for a minimum of 18 months or until death or termination of the project period with a face-to-face interview at 1 and 2 months, telephone interviews at 4, 9, 15, 21 and 27 months and face-to-face interviews including neuropsychological testing every 6 months up to 12 years. Medical records for each patient from all hospitalizations (including outside hospitals) will be reviewed at the end of their index hospitalization, after each subsequent hospitalization, after their final study **interview or end** of data collection (12 years)--to identify any hospitalizations (including recurrent delirium and repeat surgeries), intercurrent illnesses, new diagnoses, unidentified hospitalizations, or unreported deaths.

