A.3.1.2. Screening assessment: The purpose of the screening assessment is to verify subject eligibility. Based on a 10-minute patient interview along with medical record review, information will be collected to establish eligibility criteria and to rule out the presence of delirium at baseline [Modified Mini-Mental State Examination (3MS), digit span, Confusion Assessment Method (CAM), Memorial Delirium Assessment Scale (MDAS) and Delirium Symptom Interview (DSI) (*Simon 2006*)]. The screening will also complete the first stage of our two-stage process to exclude patients with dementia. All screening information will be entered into a tablet computer by the interviewer, and immediate subject eligibility will be determined based on internal algorithms to determine all inclusion and exclusion criteria, to rule out delirium and first-stage dementia, and to verify meeting frequency-matching criteria for enrollment among comparison subjects. This real-time enrollment procedure using the tablet computer has been pilot tested, and verified to be usable, efficient, and acceptable to subjects and staff.

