A.3.1.3. Baseline assessment interviews: The purposes of the baseline assessment are to describe the subjects, to document baseline neurocognitive function, to characterize baseline risk factors for delirium and cognitive decline, and to measure potentially confounding factors. This assessment will be conducted immediately following the screening assessment in eligible patients. The 80-minute baseline interview will collect information on cognitive functioning (neuropsychological test battery), demographics, education, occupation, medical diagnoses, comorbidity, medications, health habits (e.g., smoking, alcohol), hearing, mobility, basic and instrumental activities of daily living, depression, and anxiety. In a pilot study, we have verified that these interviews are feasible and tolerable in older persons. A family or caregiver interview will be conducted to establish the subject's baseline cognitive functioning, to assess for evidence of dementia [DQ (*Silverman 1987*)], and to determine any recent changes in mental status. Based on our previous and pilot studies, about 3-4% of participants will not have a family member or caregiver available to participate in these interviews; in these cases, we will approach (with the patient's consent) friends, neighbors, visiting nurses, or other reporters about the patient's baseline functioning. All enrollment and baseline assessments will be completed prior to the scheduled surgical admission.

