C.1. Inclusion Criteria: The surgical procedures selected are those which are associated with a high risk (>25%) of delirium, i.e., total hip or knee replacement, cervical laminectomy, lumbar laminectomy, lower extremity arterial bypass, thoracoabdominal aortic aneurysm repair, open abdominal aortic aneurysm repair, lower extremity amputation, or colectomy. The published literature indicates a high risk of delirium associated with vascular and orthopedic surgery and colectomy (*Balasundaram 2007, Benoit 2005, Bohner 2003, Galanakis 2001, Ganai 2007, Kudoh 2004, Mann 2000, [name]/Goldman 1994, Olin 2005, Sampson 2007, Schneider 2002*). We have reduced the number of surgical types in order to reduce the heterogeneity of risks in our study population. In addition, some high-risk procedures from these categories were excluded. Coronary artery bypass surgery was excluded, since this surgery is associated with long-term cognitive decline due to microemboli and other phenomena associated with the cardiac bypass pump. Similarly, carotid endarterectomy was excluded due to associated microembolic phenomena. Hip fracture surgery was excluded due to its non-elective nature. For this study, potential subjects will be identified from the BIDMC and BWH operating room advanced booking schedules.

C.1.1. The specific eligibility criteria are as follows: (1) Age \geq 70 years; (2) scheduled for an elective major vascular or orthopedic surgical procedure or colectomy (open, not minimally invasive); (3) planned to receive general anesthesia and to be admitted to the hospital for at least 2 days; (4) scheduled at least 7 days prior to surgery, to allow adequate time for the baseline assessment; (5) English-speaking.

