C.1.2. Exclusionary criteria are: (1) Probable dementia, other than mild impairment (by 3MS): we will implement a two-stage process to exclude all patients with probable dementia, mild-moderate impairment or greater at baseline (see details below); (2) active delirium by medical record review or initial cognitive testing; (3) any hospitalization within 3 months prior to enrollment—to minimize the risk of delirium in previous 3 months; (4) terminal condition (i.e., life expectancy < 6 months), including terminal diagnoses such as metastatic cancer, pancreatic cancer, or receiving palliative care; (5) heavy alcohol history—due to the risk of delirium tremens including documented evidence of alcohol abuse or history of alcohol withdrawal within last 6 months, and greater than 5 drinks per day (for men) or greater than 4 drinks per day (for women); (6) legal blindness and total deafness due to inability to complete neuropsychological testing (lesser degrees of vision/hearing impairment will be included); (7) History of schizophrenia or psychosis; (8) Current chemotherapy;

In the first stage of our dementia screening process, we will exclude all patients with a history of dementia or use of dementia drugs by medical record review or physician report, or with a 3MS score of <69 or its education-adjusted equivalent (correlates with MMSE score \leq 20) on the screening interview (*Tombaugh 1996*). The education-adjusted scores (*Khachaturian 2000*) are \leq 60, \leq 66, \leq 69, \leq 70, \leq 72, \leq 73 for persons with <8, 8-11, 12, 13-15, 16, 17+ years of education, respectively. For the second stage (baseline interview), patients scoring in the abnormal range on any 2 tests (> 1 SD below mean) in the neuropsychological battery will be adjudicated by an expert panel including 2 neurologists, 1 neuropsychologist, 1 geriatric psychiatrist and 2 geriatricians, with review of all study data including interviews, neuropsychological testing results, informant-rated Dementia Questionnaire (DQ, *Silverman 1987*) where available, and medical record data. The expert panel members will review cases quarterly. This 2-stage process should allow us to identify all patients with probable dementia.

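### The second-stage baseline dementia exclusion is decided quarterly on all study data, with no cut-off at admission and no masking to delirium, so it could select on exposure and early outcome

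*Protocol*

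**What the plan says.** Protocol C.1.2 sets a two-stage screen whose purpose is to "exclude all patients with probable dementia, mild-moderate impairment or greater at baseline". Stage one uses dementia history or drugs and the 3MS score. Stage two is tied to the interview held at baseline, and its trigger reads: "patients scoring in the abnormal range on any 2 tests (> 1 SD below mean) in the neuropsychological battery will be adjudicated". The decision lies with a panel of specialists, who work "with review of all study data including interviews, neuropsychological testing results, informant-rated Dementia Questionnaire"; the informant form is used if it exists, and medical records are added. On timing, "The expert panel members will review cases quarterly".

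Four other places bear on when that decision falls:

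- C.1.1 requires patients to be "scheduled at least 7 days prior to surgery, to allow adequate time for the baseline assessment".
- A.3.1.2 describes an immediate tablet check of eligibility, which serves "to rule out delirium and first-stage dementia". It does not cover stage two.
- A.3.1.3 says "All enrollment and baseline assessments will be completed prior to the scheduled surgical admission". It does not say that the panel's decision will be.
- A.2 says that in the index stay "patients will be assessed daily for the development of delirium, the major predictor variable". A.3.1.4 makes admission zero-time, and the first cognitive retests follow at 1 and 2 months.

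The protocol sets no date limit on what the panel may read, does not mask it to delirium, and does not say what happens to a patient found ineligible after surgery.

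**The concern.** A baseline eligibility criterion should be settled on information that exists before the exposure. Here the panel may meet when the patient has already had surgery, has daily delirium ratings on file and, in some cases, has a retest on the battery that supplies the primary outcome. Each kind of material named in C.1.2 is also produced after admission: interviews and batteries at 1 and 2 months, the index-stay chart review (which itself rates delirium), and later informant questionnaires.

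If those data inform the judgement, entry to the cohort depends on exposure and early outcome. That is selection after zero-time, and covariate adjustment does not remove it. It also touches a strength the protocol claims for itself. The background section faults earlier studies for including dementia patients and for having no assessment before delirium, and B.4.2 presents pre-delirium baseline assessment as an advance.

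**Working it through.** **1. The plan's own power figures (B.1.1).** Inputs: 400 patients with complete 18-month data, 25% delirium (100 against 300), type I error 5% (taken as two-sided).

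SE = sqrt(1/300 + 1/100) = 0.1155 SD; power = Phi(d/SE - 1.96).

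- d = 0.61: 0.61/0.1155 = 5.28, power 99.96% (plan: 100%).
- d = 0.33: 0.33/0.1155 = 2.86, power 81.5% (plan: more than 80%).

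Both figures reproduce. This point disputes neither.

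**2. When does the decision fall?** Assumption: baseline interviews are spread evenly over a review cycle of Q = 91.3 days. With L days from baseline interview to admission, the share whose next review falls after admission is 1 - L/Q. For the 1-month retest it is 1 - (L + 30.4)/Q, and for the 2-month retest 1 - (L + 60.9)/Q.

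| L (days) | After admission | After 1-month retest | After 2-month retest |
|---|---|---|---|
| 7 | 92% | 59% | 26% |
| 14 | 85% | 51% | 18% |
| 21 | 77% | 44% | 10% |
| 30 | 67% | 34% | 0.4% |

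The 7 days in C.1.1 is a minimum for booking, and the protocol gives no distribution. The interval from interview to admission can be shorter or much longer. At L = 60 the first share is 1 - 60/91.3 = 34%, and it reaches zero at about 91 days.

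**3. Which way could the estimate move?** Illustration only; every input other than the -0.61 SD is assumed. Simulated patients have a standard normal baseline score b. Delirium has log-odds -1.2 - 0.4b, giving about 24%. Change is -0.61 x delirium plus unit-variance noise. The lowest 30% on b go to the panel, which removes 2%, 5% or 10% of the whole cohort from that pool. The table gives the baseline-adjusted delirium effect among those kept.

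| Panel removes first | 2% | 5% | 10% |
|---|---|---|---|
| Lowest baseline score | -0.609 | -0.611 | -0.610 |
| Delirious patients, regardless of course | -0.611 | -0.613 | -0.613 |
| Largest decline, delirium not considered | -0.562 | -0.536 | -0.540 |
| Delirious decliners | -0.492 | -0.411 | -0.616 |
| Non-delirious decliners | -0.676 | -0.746 | -0.815 |

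The fourth row returns to about -0.61 at 10% because the rule has then used up the delirious patients in the pool. Delirium falls from 23.9% to 15.7% of those kept, so 0.239 - 0.9 x 0.157 = 0.098 of the cohort removed was delirious. The last three rules rank patients on the final change itself. A real panel would see at most early status, so these rows show direction and tend to overstate size.

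**The case against.** The strongest reply is that the protocol nowhere says post-operative data are used to exclude anyone. Stage two is labelled as belonging to the baseline interview, its target is impairment at baseline, and the items listed match what screening and baseline collect. In-hospital delirium ratings and retests are not named. Dementia that emerges later is treated as an outcome: A.6.1 sends such patients to the clinical outcomes sub-study, and Table 2 lists a consensus dementia diagnosis as a secondary outcome. Packet contents and masking often sit in an adjudication manual, and a sensitivity analysis may sit in an SAP that is not shown.

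Much of this stands. Use of later data is permitted by the wording, not stated. But the label fixes which tests trigger review, not what the panel then reads, and the scope written down is all study data. A quarterly timetable also cannot reliably deliver a decision before a surgery booked 7 days ahead. That combination is fixed in the protocol itself, so it is more than detail left for elsewhere.

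A reader might go further and infer that the delirium effect is biased toward zero and that power is lost. The documents do not support that. Attenuation needs delirious decliners, or decliners in general, to be preferentially called demented. A panel that attributes decline after delirium to the delirium would exclude non-delirious decliners instead, and the estimate would move away from zero. Removing genuine baseline dementia also removes confounding, which is the purpose of the criterion. A reader might also infer that most cases would be reviewed after both retests; the table above shows that few would be after the 2-month battery unless lead times are short.

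**Conclusion.** The gap is real, of moderate weight, and cheap to close. As written, a baseline exclusion can be decided after zero-time with delirium status on file: for about 67% to 92% of adjudicated cases at intervals of 30 down to 7 days, and for 34% to 59% after the 1-month retest. These shares rest on evenly spread baseline interviews and on assumed intervals.

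The effect on the delirium estimate has no derivable size or sign, because the protocol gives no number adjudicated, no number excluded and no lead-time distribution. The range of -0.41 to -0.75 around a true -0.61, with 2% or 5% of the cohort removed, is an illustration and not an estimate. Power for the hypothesised effect is not in question: at the planned 300/100 split, an effect of 0.40 SD still has 93.4% power, before any loss of delirious patients through exclusion. What is at stake is whether the estimate can be read as the effect of delirium in a cohort defined before delirium occurred.

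**What to change.** In C.1.2:

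- State that stage-two adjudication uses only data dated before the index admission: the screening interview, baseline battery, baseline informant questionnaire and pre-admission records. Packets are masked to delirium and to everything later. A late meeting then does no harm, since the decision cannot depend on what followed.
- State that patients adjudicated after admission stay in follow-up with a flag. Repeat the primary analysis including those classified as probable dementia, as a sensitivity analysis.
- For decisions already taken, record the decision date and what the panel saw, and report the number adjudicated and the number excluded by delirium status.

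The cost is some packet preparation and one extra analysis, with no new visits, tests or panel members. If the panel already works this way, one sentence in C.1.2 settles the point.
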